In summary, the behavioral component of the proposed multi-modal treatment will be a PILI that targets improvements in spoken language and challenging behavior for 10- to 17-year-olds with FXS by increasing PVR within picture-book based storytelling episodes. Finally, parents/caregivers will be encouraged to use the targeted strategies in other everyday interactions with their child. The intervention will be delivered to parents/caregivers in their homes by way of VTC. Considerable preliminary work will need to be conducted, however, before combining it with lovastatin. Thus, we propose to spend the first 18 months of the project conducting two small-scale studies of PILI alone. The first phase (Phase 1) of the PILI study was designed to collect preliminary data, enrolled three mothers and their sons and will be completed by end of December 2014. NIH has requested that we continue to test the preliminary efficacy of the behavioral intervention using a small N group design study prior to implementing the phase of the intervention which includes the drug Thus, the second phase of the study (Phase 2) will be a group design (N=30) with randomized assignment to a Treatment Group or a Wait List Comparison Group. Participants in the Treatment Group receive the behavioral intervention and the Wait List Comparison Group receives treatment as usual. The final phase of the study (Phase3) will be a clinical trial (N=50) in which participants are randomly assigned to receive the behavioral intervention alone or in combination with Lovastatin.

5) Inclusion and Exclusion Criteria

Subjects will be screened initially through a pre-screening form either over the phone or in person at the MIND Institute. If the subject is eligible based on the responses to the pre-screening form they will be given the option of scheduling a screening visit to complete screening assessments and confirm if language level and overall functioning are adequate to participate in the trial.

Inclusion Criteria:

- 1. Documentation of a full mutation with absence or deficient FMRP levels.
- 2. Males and females ages 10 through 17 years (Consent Forms A and B). Note:

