We propose to conduct a study of the efficacy of the adapted PILI program during the first 18 months of the IDDRC funding period. We expect to enroll up to 30 participants and employ a series of single-case designs and PILI vs. treatment-asusual group comparison design, with the latter group receiving no intervention other than what they are already receiving in the community and will participate only in pre- and post-treatment assessments. The treatment-as-usual participants will have the opportunity to go into the multimodal study, or clinical trial portion of the project, which will serve to maintain the participant's commitment and participation in the absence of treatment. Note that there are many reasons to believe that the adapted PILI program will be efficacious. These include evidence from other languagedisordered populations of the utility of narrative as a good context for intervention for this age group and also evidence of the importance of parental verbal responsiveness (as embodied in PILI) to language development throughout childhood and into adolescence for individuals with FXS from longitudinal observational studies. Following the PILI only component, we will open enrollment into the clinical trial utilizing consent form B, and begin randomizing participants to lovastatin or placebo while receiving PILI.

In addition to the above studies, a separate study (ICF D) examining the feasibility of implementing PILI in a younger population of boys with FXS (ages 5- to 8-years of age) and their biological mothers will be conducted. We expect to recruit approximately 3 children whose participation will last approximately 3-6 months. The study implemented for this younger age group will follow similar procedures as described for the older children in consent form A, with the exception that the study materials will be adapted for children who are verbal but who are at the beginning stages of language development. Participation in this study will not require any visits to the MIND Institute; all information will be gathered through questionnaires and interactions via SKYPE.

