ix. Child Spoken Language: ICF A and B

The conversation and narration procedures described in Preliminary Studies will be administered at the baseline and post-treatment visits. Alternate versions of conversation and narration materials will be administered at the two visits and counterbalanced.

Neurobehavioral Analysis Core staff blind to hypotheses and participant characteristics will transcribe/code. A spoken language ability composite will be obtained for each assessment time by taking a weighted mean of variables reflecting talkativeness, fluency, intelligibility, vocabulary diversity, and syntactic complexity in combined narrative and conversational samples. This composite will provide a broad-based and robust measure of spoken language ability and serve as the primary outcome measure. Exploratory analyses will evaluate the separate contributions of the variables included in the composite (30 min).

DOS 5.1 (Version Date: 07-Nov-2017)

x. The Social Communication Questionnaire (SCQ): ICF D

A widely used informant report checklist that evaluates communication and social skill deficits common to those with symptoms of autism. This brief questionnaire will be completed by the participant's parent/caregiver (10 min).

xi. The Vineland Adaptive Behavior Scales (VABS): ICF D

The VABS is a widely used informant report checklist that will be used to assess four domains: communication; self-care; social skills; and maladaptive behavior. It will be completed by the participant's parent/caregiver (30 min).

xii. Childhood Autism Rating Scale, Second Edition (CARS-2): ICF D

An examiner completed behavioral rating scale used to evaluate symptoms of autism following a direct observation of a child. The parent-child structured interaction will be used as the context which is evaluated for this measure.

xiii. The Aberrant Behavior Checklist (ABC): ICF A, B, and D

A behavior rating scale completed by the parent/caregiver that is frequently used to examine treatment effects on challenging behaviors for individuals with FXS. The scale is comprised of 58-items in the following domains: (1) irritability, agitation, crying; (2) lethargy, social withdrawal; (3) stereotypic behavior (4) hyperactivity, noncompliance; and (5) inappropriate speech (15 min). The Sansone et al. (2011) FXS-normed ABC scoring measures will be used. The social avoidance subscale score will be a secondary clinical endpoint.

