Half of the participants will receive the Parent-Implemented Language Intervention (PILI) under consent form A, the remaining half of participants will have the option to participate in the clinical trial portion of the study under consent form B, at which point they will be guaranteed to receive the PILI intervention.

All participants will receive the Parent-Implemented Language Intervention (PILI) under the clinical trial portion of the study, consent form B. In addition to PILI, half of the patients will be randomized to take lovastatin and may experience a beneficial response to lovastatin including heightened response to PILI with language improvements and reduction of problematic behaviors of FXS including ADHD,

aggression, and anxiety. All participants under consent form B will also benefit by receiving physical exams, cognitive assessments, and blood tests.

18) Vulnerable Populations

The patient population to be studied is developmentally disabled children with fragile x syndrome. We have done research with developmentally disabled and cognitively impaired individuals of all ages for many years. The consent process for individuals without the cognitive ability to consent will be completed by the parent, caregiver, or legally authorized representative (LAR), and no procedures will be done with any subjects without consent of either subject or parent/caregiver/LAR.

19) Sharing of Results with Subjects

At the conclusion of the study, the possible medical benefit from the study will be reviewed with the subject and his or her parent/guardian. Any laboratory work considered standard of care will be available for patients at their request. Psychological assessment scores may be communicated to the subjects if it does not impact future testing. If a subject has to be unblinded for emergency purposes then the subject will be notified by the principal investigator or study physician. Unblinding will be conducted in accordance with the MIND Institute's SOP# 500-014: Study Subject Unblinding Process. The results of the study may also be published or presented at scientific meetings including peer reviewed scientific journals that will be made publicly available through PubMed Central. In addition, after publication the results will be posted on the MIND Institute website under clinical trials

20) Setting

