Costs of travel may include, but are not limited to economy airfare, car mileage, lodging, bridge tolls, parking garage fees, taxis, rental cars or gas reimbursement for rental cars. Reimbursement will be based off of paid receipts submitted by families per UCDMC reimbursement policy. Travel reimbursement is based off of employee reimbursement guidelines enforced by the Department of Psychiatry and Behavioral Sciences and University policy. Reimbursement checks will typically be mailed 4-10 weeks from submission of paid receipts following the completed study visit.

26) Consent Process

Patients will be recruited and consented at the UC Davis MIND Institute. The consent will conform to HRP-90 and HRP-091.

The permission will be obtained from both parents unless one parent is deceased, unknown, incompetent, or not reasonably available, or when only one parent has legal responsibility for the care and custody of the child. If the child has the cognitive capacity to assent, then they will be assented to participate. Study staff will assess the capacity to consent using the Capacity Assessment Checklist for Informed Consent with Cognitively Impaired Subjects. Parents or LARs whose child turns 18 throughout the course of the study will be consented with the surrogate decision maker form.

All parents or LARs will sign a HIPAA authorization for research.

27) Process to Document Consent in Writing

We will be following "SOP: Informed Consent Process for Research, HRP-090" and "SOP: Written Documentation of Consent, HRP-091."

28) Drugs or Devices

The investigational product will be dispensed by bottle number by the Investigational Drug Services Pharmacy (IDS). All investigational product supplies must be kept in a secure locked cabinet or location, with access limited to authorized clinical investigation personnel. The contents of each bottle will be blinded using labels that contain a unique bottle number. The randomization schedule will match a subject number to the unique bottle number and an appropriate dose. Upon completion of screening evaluations for each subject, the Investigator or appropriate designee will contact IDS to randomize subject and dispense investigational product. The Pharmacist at IDS will select the correct bottle of investigational product and distribute the bottle to the Investigator or designee. Only IDS will be unblinded as to the contents of each bottle of investigational product.

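### Up to 15 of the 50 Phase 3 children may already have done the primary language task twice as Phase 2 controls, and the plan names this neither as a stratum nor as a covariate

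*Combined protocol and SAP*

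**What the plan says.** **Roll-over route.** Section 4 describes the second phase: "Phase 2) will be a group design (N=30) with randomized assignment to a Treatment Group or a Wait List Comparison Group". Section 11 says that the comparison children "will participate only in pre- and post-treatment assessments", and it presents later entry to the drug trial as a way of keeping them committed. Section 17 repeats the offer: "the remaining half of participants will have the option to participate in the clinical trial portion of the study under consent form B". Section 5 gives no washout or exclusion for earlier participation.

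**Shared measures.** The Child Spoken Language procedure (section 11(a), child measure ix) yields the primary composite and is marked for consent forms A and B. "Alternate versions of conversation and narration materials will be administered at the two visits and counterbalanced". The parent/child narrative Task 1, also marked for forms A and B, has two named picture books, version A and version B.

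**Randomisation and analysis.** Section 11(b) assigns randomisation to the pharmacy's computer algorithm. It refers to stratification variables that are not listed in the text at hand, and says that significant group differences on these or other variables will be handled by adding covariates to the primary analyses. Section 28 adds: "The randomization schedule will match a subject number to the unique bottle number and an appropriate dose". Section 10 specifies an ANCOVA adjusted for the baseline value of the outcome. The Hypothesis 1b regressions adjust for the baseline parent and child measures, with parent confounders also to be evaluated. None of these places names earlier Phase 2 participation.

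**The concern.** Alternating task versions over two visits keeps a child from meeting the same material twice. A roll-over child has four visits: two in Phase 2 and two in Phase 3. If the primary task has only two versions and Phase 3 reuses them, both have been used before the Phase 3 baseline, and the safeguard does not work for that child. For Task 1 the point is firmer. Only two books are named, so a roll-over family will have seen both, provided that the pair was spread over the two Phase 2 visits as the counterbalancing implies. Task 1 supplies parent variables of the kind that Hypothesis 1b tests.

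Baseline adjustment absorbs whatever practice is already present at the Phase 3 baseline. It does not absorb a different change from there to Week 20 between children on a third and fourth exposure and children on a first and second. Such a difference goes into the residual and, by chance, into the contrast between arms. The trial is small, so cheap precision is worth having.

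**Working it through.** **Inputs from the protocol.** Phase 3 has N = 50 (section 4), and "half of the patients will be randomized to take lovastatin" (section 17), so 25 per arm. Phase 2 has N = 30, half of them controls (sections 4 and 17). The form A cap is 30 (section 6) and covers Phases 1 and 2; Phase 1 "enrolled three mothers and their sons". Section 10 states 80% power for an effect of 0.6 SD at two-sided alpha 0.05.

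**Assumed, because the protocol gives neither.** δ is the roll-over minus new difference at Week 20 given baseline, in outcome SDs: 0.2 to 0.5. r is the baseline-outcome correlation: 0.5 to 0.67.

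**1. The plan's power figure.** With 25 per arm and no gain from baseline, 0.6 × √(25/2) = 2.12, and Φ(2.12 − 1.96) = 56%. The stated 80% is reached if r is about 0.65 (normal approximation) to 0.67 (t). I use r ≈ 0.66 below, so that the stated power holds.

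**2. Number of roll-overs.** 30/2 = 15, and 15/50 = 30%. If the three Phase 1 children count against the cap, Phase 2 has 27 children and 13 or 14 controls.

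**3. Chance imbalance.** With K = 15 allocated without regard to status, the number in one arm is hypergeometric (50, 15, 25). A 10:5 split or worse has probability 0.22, and 11:4 or worse 0.06. The SD of the between-arm difference in roll-over share is 0.13. With K = 13, a 9:4 split or worse has probability 0.20.

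**4. Would the section 11(b) rule act?** Fisher's exact two-sided p is 0.22 at 10:5, 0.06 at 11:4 and 0.012 at 12:3. At the 5% level the rule first acts at 12:3.

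**5. Shift of the estimate at 10:5.** (10/25 − 5/25) × δ = 0.20δ, which is 0.04, 0.06 and 0.10 SD for δ = 0.2, 0.3 and 0.5. The standard error is √(2(1 − r²)/25), or 0.245 at r = 0.5 and 0.210 at r = 0.67. The shift is therefore between 0.04/0.245 ≈ 0.2 and 0.10/0.210 ≈ 0.5 standard errors.

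**6. Residual variance and power (K = 15, r ≈ 0.66, normal approximation).** Omitting the indicator adds 0.3 × 0.7 × δ² = 0.21δ² to a residual variance of 1 − r² ≈ 0.57.

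| δ | Variance increase | Power, status ignored | Power, stratum and covariate | Loss (points) |
|---|---|---|---|---|
| 0.2 | 1.5% | 79.8% | 80.3% | 0.6 |
| 0.3 | 3.3% | 79.0% | 80.3% | 1.3 |
| 0.5 | 9.2% | 76.8% | 80.3% | 3.5 |

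Losses are taken before rounding. With r = 0 they are 0.4, 0.8 and 2.1 points from a base of about 56%. Steps 5 and 6 are two views of the same noise and should not be added.

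**7. Covariate without the stratum.** Under unstratified allocation the expected squared correlation between arm and a binary covariate is 1/49, so adjustment itself costs about 2% in variance plus one degree of freedom. By simulation, the covariate alone loses up to about 1 power point when δ is 0.2 or less, breaks even near 0.3, and gains about 2 to 3 points at 0.5. Stratum plus covariate costs about 0.2 points or less if there is no difference, and otherwise gains roughly 0.5 to 3 points.

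**The case against.** Four stronger readings are tempting, and the protocol supports none of them.

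- *Roll-over children have certainly used up every version of the primary task.* Section 11(a) gives neither the number of versions nor a statement that Phase 3 reuses them. It defers to a description of preliminary studies that is not in the text at hand. Two versions is a reasonable inference from two counterbalanced visits, but only the Task 1 books are explicitly two, and Task 1 is not the primary outcome.
- *The plan makes no provision at all.* Section 11(b) refers to stratification variables and has a covariate rule. The section 28 sentence concerns dispensing and does not show that allocation is unstratified. What stands is that earlier participation is not named and that the rule would usually not act.
- *The drug estimate is biased.* It is not. Roll-over children are randomised like the others, type I error holds, and chance imbalance is already reflected in the ANCOVA standard error.
- *Fifteen children will roll over.* That is a ceiling. It needs a full Phase 2, every control accepting, and every one meeting the Phase 3 exclusions.

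The best remaining objection is that δ is unknown in size and direction. The outcome is a composite from conversation and narration samples, not a test with answers to memorise, and the interval between the Phase 2 post-test and the Phase 3 baseline is not given. A small δ is quite possible, and then little is lost. That limits the weight of the point but does not remove it, because stratum plus covariate costs almost nothing even when δ is zero.

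**Conclusion.** The point holds as a minor efficiency improvement. A known, binary, pre-randomisation characteristic that may apply to up to 30% of the Phase 3 sample is left out of the named strata and covariates, and the conditional rule in section 11(b) would miss the likely imbalances. The power loss is about 0.5 to 4 points for an assumed difference of 0.2 to 0.5 SD, with 15 roll-overs and a baseline correlation near 0.66; it is smaller with fewer roll-overs or a weaker correlation. Validity is not in question. The failure of the alternate-version safeguard on the primary task depends on there being only two versions that are reused, which the sponsor can confirm or rule out in one sentence.

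**What to change.** 1. In section 11(b), list the stratification variables and add prior Phase 2 participation (yes/no).
2. In section 10, include it as a prespecified fixed covariate in the primary ANCOVA and the Hypothesis 1b regressions, instead of relying on the significance-triggered rule.
3. In section 11(a), state how many versions of the conversation and narration materials exist and whether Phase 3 reuses those from Phase 2. At the Phase 3 baseline, give each roll-over child the version seen longest ago, and record version order for every child.

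**Cost.** One degree of freedom, one more stratum in the pharmacy schedule and a few sentences; the only new item to record is version order. With 50 children, the sponsor should check that the extra stratum does not leave cells too sparse alongside those already intended. If randomisation has begun without the stratum, the covariate alone pays off only if the difference exceeds about 0.3 SD. That choice should be made and documented before unblinding.
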